**Number of Subjects (planned):**

Up to 30 subjects are planned.

**Investigational Product, Dosage and Mode of Administration:**

Based on safety and efficacy data from previous studies, all subjects enrolled into this study will receive BCX9930 400 mg twice a day, with or without food.

**Duration of Treatment:**

Each subject will be eligible to receive study drug (BCX9930) under this protocol for up to 96 weeks as long as the investigator believes it is in the subject's best interest to continue treatment, or until the subject has access to other therapy for PNH, whichever comes first. Treatment with BCX9930 will be discontinued for subjects who are deriving no meaningful clinical benefit, or who experience an unacceptable drug-related AE or are otherwise intolerant of study drug.

**Reference Therapy, Dosage and Mode of Administration:**

Not applicable.

**Statistical Methods:**

A detailed statistical analysis plan (SAP) will be developed to describe the methods of analyses and summaries, including all endpoints, time points, populations, missing data, etc. Deviations from the analyses outlined in the SAP will be described in the clinical study report.

## List of Abbreviations

**Table 1: List of Abbreviations and Definitions of Terms**

Abbreviation	Term
AE	adverse event
ARC	absolute reticulocyte count
BID	twice daily
CTCAE	Common Terminology Criteria for Adverse Event
DMC	data monitoring committee
eCRF	electronic case report form
Hb	hemoglobin
ICH	International Council for Harmonisation
LDH	lactate dehydrogenase
MedDRA	Medical Dictionary for Regulatory Activities
PNH	paroxysmal nocturnal hemoglobinuria
RBC	red blood cell
SAE	serious adverse event
SAP	statistical analysis plan
TEAE	treatment-emergent adverse event
WBC	white blood cell

## 1. INTRODUCTION

BioCryst stopped development of BCX9930 in December of 2022 based on changes in the competitive environment. The purpose of this statistical analysis plan (SAP) is to describe the planned analyses and data displays to be included in the abbreviated clinical study report (aCSR) for Study BCX9930205 (Study 205).

Protocol Revision Chronology:		
Protocol v1.0	03 March 2022	Original
Protocol v2.0	05 August 2022	Amendment 1
Protocol v3.0	23 February 2023	Amendment 2
Protocol v4.0	27 July 2023	Amendment 3

This SAP was developed in accordance with the International Council for Harmonisation (ICH) E9 guideline. The purpose of this document is to provide details on the statistical methodology used to meet the objectives for Study 205. Study population definitions, derivations of variables, handling of missing data, and other information necessary for analysis of study data are provided. Planned tables and listings are specified.

The document may evolve over time, for example, to reflect the requirements of protocol amendments or regulatory requests. However, the final SAP must be finalized, approved by the sponsor, and placed on file before database is locked. Deviations from the final approved plan will be noted in the CSR.

## 2. STUDY OBJECTIVES AND ENDPOINTS

### 2.1. Objectives

The objectives of this study are:

- To provide continued access to BCX9930 for subjects with PNH who have benefited from treatment with BCX9930 in another BioCryst-sponsored study and who, in the opinion of the investigator, would benefit from continued treatment with BCX9930, and who do not have access to other effective treatment options.
- To monitor the safety of BCX9930 in subjects continuing to receive BCX9930 for the treatment of PNH.

### 2.2. Endpoints

The endpoints of this study are:

- Subject incidence of graded treatment-emergent adverse events (TEAEs) and laboratory abnormalities.

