**Table 3: Clinical Laboratory Evaluations**

Serum Chemistry	Urinalysis with Microscopy a
Albumin	Albumin
Alanine aminotransferase (ALT) (SGPT)	Bilirubin
Alkaline phosphatase (ALP)	Blood
Amylase b	Creatinine
Aspartate aminotransferase (AST) (SGOT)	Glucose
Bilirubin (total and direct)	Ketones
Blood urea nitrogen (BUN)	Leukocytes
Calcium	Nitrites
Chloride	pH
Cholesterol (total, high- and low-density lipoprotein)	Protein
Creatine (phospho)kinase (C[P]K)	Specific gravity
Creatinine (sCr)	Urine albumin to creatinine ratio (uACR)
Glucose	Urobilinogen
Haptoglobin	Pregnancy/Menopause
Lactate dehydrogenase (LDH)	Follicle-stimulating hormone (FSH)
Magnesium	Urine pregnancy test c
Potassium	Coagulation/Fibrinolysis
Sodium	Activated partial thromboplastin time (aPTT)
Protein (total)	Prothrombin time (PT)
Triglycerides	International normalized ratio (INR)
Uric acid	Thrombin time
Hematology	Other Testing
Hemoglobin (Hb)	Estimated glomerular filtration rate(eGFR) d
Hematocrit (Hct)	PNH RBC clone size (total)
Mean corpuscular hemoglobin (MCH)	PNH WBC clone size
Mean corpuscular hemoglobin concentration (MCHC)	Varicella-zoster virus (VZV) immunoglobulin G (IgG) titer (where appropriate)
Mean corpuscular volume (MCV)	Hepatitis B virus (HBV), hepatitis C virus (HCV), human immunodeficiency virus (HIV) viral load (where appropriate)
Platelet count (PLT)	
Red blood cell (erythrocyte) count (RBC)	
Reticulocyte count	
White blood cell count (WBC) with differential	

Abbreviations: DNA = deoxyribonucleic acid; PNH = paroxysmal nocturnal hemoglobinuria; RNA = ribonucleic acid; SGOT = serum glutamic-oxaloacetic transaminase; SGPT = serum glutamic-pyruvic transaminase.

Note: Some analytes may not be analyzed, depending on the availability of validated assays at the designated regional central laboratory

a Reflex to microscopy if dipstick is abnormal. For local laboratory testing, urinalysis analytes may be different.

b If amylase is elevated, reflex to lipase.

c For women of childbearing potential (or as required by local or institutional practice).

d To be calculated by the designated central reference laboratory using the Chronic Kidney Disease Epidemiology Collaboration (CKD-EPI) equation using the serum creatinine method ([Levey and Stevens 2010](#)).

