### 13.3.4. Analysis of Safety Variables

Safety endpoints will be summarized and will include, at a minimum, the proportion of subjects 1) with TEAEs; 2) who discontinue due to a TEAE; 3) with treatment-emergent SAE; 4) with a Grade 3 or 4 TEAE; and 5) with Grade 3 or 4 laboratory abnormalities.

AEs will be mapped to a Medical Dictionary for Regulatory Activities (MedDRA, Version 24.0) preferred term and system organ classification. The occurrence of TEAEs will be summarized using MedDRA preferred terms, system organ classifications, and severity. In addition to severity, AEs and SAEs will also be summarized based on investigator assessment of relationship to study drug.

For all analyses of change from baseline, the baseline is the baseline value for the current study.

Descriptive statistics for vital signs, weight, and clinical laboratory results will be presented by study visit. Laboratory abnormalities will be graded according to CTCAE scales (Version 5.0, 27 November 2017). The number and percentage of subjects experiencing treatment-emergent graded laboratory toxicities will be summarized. Laboratory toxicity shifts from baseline to the worst post-baseline value as well as to the last visit will be summarized.

The number and percentage of subjects having elevations in ALT, AST, or bilirubin abnormalities in relation to fold above ULN will be summarized according to the US FDA's Premarketing Clinical Evaluation on Drug-Induced Liver Injury Guidance for Industry ([FDA 2009](#)).

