#### 9.1.1. Tables

Title		Population
Study Population Section		
Tables		
14.1.1	Subject Disposition	All Subjects
14.1.3	Demographic and Baseline Characteristics	Safety Population
14.1.5.1	Concomitant Medications	Safety Population
14.1.6.1	Exposure to Study Treatment	Safety Population
Efficacy Section		
Tables		
14.2.1.1	Observed and Change from Baseline Hemoglobin (g/dL) by Treatment Group and Visit	Safety Population
14.2.2.3	Observed, Change from Baseline, and Percent Change from Baseline LDH by Visit	Safety Population
Safety Section		
Tables		
14.3.1.1	Overall Summary of Treatment-emergent Adverse Events	Safety Population
14.3.2.1	Treatment-emergent Adverse Events by MedDRA System Organ Class and Preferred Term	Safety Population
14.3.2.3.1	Serious Treatment-emergent Adverse Events by MedDRA System Organ Class and Preferred Term	Safety Population
14.3.2.3.2	Non-serious Treatment-emergent Adverse Events by MedDRA System Organ Class and Preferred Term	Safety Population

Title	Population
14.3.2.4	Renal Treatment-emergent Adverse Events by System Organ Class and Preferred Term: Events in the Acute Renal Failure SMQ, Chronic Kidney Disease SMQ, and Tubulointerstitial Diseases SMQ
14.3.2.5	Hepatic Treatment-emergent Adverse Events by System Organ Class and Preferred Term: Events in the Drug related hepatic disorders - comprehensive search SMQ

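### SAP 2.2 keeps the incidence of laboratory abnormalities in the endpoint, but none of the 12 planned tables reports it, and SAP Section 9 does not itemise the protocol laboratory summaries that were cut

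*SAP*

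**What the plan says.** SAP 2.2 gives the endpoint as "Subject incidence of graded treatment-emergent adverse events (TEAEs) and laboratory abnormalities". Protocol 6.2 and the technical summary at the front of the SAP carry a longer version that also covers vital signs and physical examination. SAP 2.2 therefore narrows the endpoint but leaves the laboratory component in.

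Protocol 13.3.4 sets out how that component is to be reported. Its minimum list of five subject proportions ends with the proportion "with Grade 3 or 4 laboratory abnormalities". It then adds three more items:

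- A subject count for graded results: "The number and percentage of subjects experiencing treatment-emergent graded laboratory toxicities will be summarized".
- A summary of how grades moved against baseline, once to each subject's worst later value and once to the final visit.
- For the liver tests, a second subject count: "The number and percentage of subjects having elevations in ALT, AST, or bilirubin abnormalities in relation to fold above ULN will be summarized".

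Separately, for continuous values, it says "Descriptive statistics for vital signs, weight, and clinical laboratory results will be presented by study visit".

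On the SAP side, Section 1 limits the document to an abbreviated clinical study report. Section 8 says that safety data will be shown in listings, and its subsections 8.1 to 8.2.2.4 specify adverse event tables only. Section 9 states in one sentence that, because development stopped, only variables relevant to the abbreviated report will be summarised and listed. The display lists follow in 9.1.1 and 9.1.2. The laboratory tables there are "Observed and Change from Baseline Hemoglobin (g/dL) by Treatment Group and Visit" and a similar one for LDH. The laboratory listings are 16.2.6.1 (hemoglobin and LDH) and 16.2.8 (Grade 3 or 4 abnormalities).

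**The concern.** An endpoint worded as subject incidence needs a count, a denominator and a rule for what counts. If the SAP is followed exactly, the adverse event half of the endpoint gets all three and the laboratory half gets none.

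Monitoring safety is one of the study's two objectives. The protocol singles out renal toxicity (5.2.1, 12.5.2) and liver injury (12.5.1), and both are followed through creatinine, ALT, AST and bilirubin. Under the plan none of these has a laboratory summary table.

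A second, smaller matter is traceability. Section 9 is the place for changes from protocol-specified analyses, and it names no dropped laboratory analysis. The reader is left to judge whether each absence was a decision or an oversight.

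**Working it through.** There is no sample size, power or alpha figure to reproduce. The check is a count and a side-by-side comparison.

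**1. Tables in SAP 9.1.1.** Study population 4, efficacy 2, safety 6: 4 + 2 + 6 = 12. Two use laboratory data (14.2.1.1 hemoglobin, 14.2.2.3 LDH). Both are continuous, by visit, and in the efficacy section. Tables giving the incidence of laboratory abnormalities: 0 of 12. The list carries no redaction, so the gap is not an artefact of removed text.

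**2. Protocol 13.3.4 commitments against SAP displays.**

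| Protocol 13.3.4 | SAP table | Nearest SAP display |
|---|---|---|
| Proportion with Grade 3 or 4 abnormality | none | Listing 16.2.8 |
| n (%) treatment-emergent graded toxicity | none | Listing 16.2.8, Grades 3 and 4 only |
| Shifts to worst and to last value | none | none |
| n (%) ALT/AST/bilirubin by fold above ULN | none | none |

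None of the four has a table. By-visit descriptive statistics, a further protocol item, survive for hemoglobin and LDH only. They are not incidence, so they do not bear on the endpoint. They belong only in the list of changes.

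**3. The protocol's minimum list against SAP 8.1.** Subjects with a TEAE: present. Discontinuation due to a TEAE: present. Serious TEAE: present. Grade 3 or 4 TEAE: present. Grade 3 or 4 laboratory abnormality: absent. So 4 of 5 are tabulated, and the missing one is the laboratory item.

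**4. What the listings allow.** Subjects with Grade 3 or 4 values can be counted by hand from Listing 16.2.8. Outside hemoglobin and LDH, no named display shows Grade 1 or 2 results or fold-ULN categories.

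**5. Whether the adverse event tables can stand in.** Protocol 11.5.4 sends results judged clinically significant to the adverse event form. Protocol 12.1.1 excludes results that prompt no further treatment, visit or monitoring. The renal and hepatic tables (SAP 8.2.2.3 and 8.2.2.4) then select adverse event terms by SMQ. They give the incidence of reported events, which is a different quantity from the incidence of graded laboratory abnormalities. A creatinine, ALT or bilirubin change not reported as an event enters no summary table.

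**6. Whether SAP 9.1 leaves room.** It allows retitling, renumbering, extra supporting listings and split displays without a revision. It does not mention new summary tables.

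**The case against.** The strongest reply is that the reduction is deliberate and disclosed. Development had ended, and SAP Sections 1, 8 and 9 all say that reporting is abbreviated. The study has at most 30 subjects, one treatment and no hypotheses. Listing 16.2.8 is the chosen display for severe abnormalities, and the safety-population size will be known from other tables, so the Grade 3 or 4 proportion is a short hand count. Clinically significant results reach the adverse event tables, and a DMC oversees safety. Much of this stands. It justifies dropping shift tables and most by-visit statistics. It does not explain why SAP 2.2 removed vital signs and physical examination, kept laboratory abnormalities, and then planned no summary of them. SAP 5.6.7 itself speaks of endpoint data being summarised.

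Three stronger readings are tempting and are not supported:

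- *The cuts are concealed.* They are not. The display lists sit inside Section 9, and comparing them with protocol 13.3.4 shows what went. The fair criticism is that they are not itemised.
- *Laboratory safety signals would be lost.* The adverse event route and Listing 16.2.8 make that too strong. Protocol 12.5.1, for example, asks for ALT above 3 × ULN to be confirmed, so such a value may well be recorded as an event.
- *Four separate tables are missing.* The Grade 3 or 4 proportion and the graded-toxicity count overlap, and one table can carry both.

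A reader might also lean the other way and say that every result will be listed, so only the summary is missing. Protocol 13.3.2, SAP 5.6.7 and SAP Section 8 contain general sentences to that effect. But SAP 9.1.2 names only the two laboratory listings, and Section 9 restricts what is listed as well as what is summarised. Fuller listings are possible; the plan does not commit to them.

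**Conclusion.** The point holds. As written, the SAP does not report a component of its own endpoint: 0 of 12 tables give laboratory-abnormality incidence, none of the four protocol summaries above has a table, and 1 of the protocol's 5 minimum safety proportions is untabulated. Section 9 gives a general reason and no itemised list.

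This should be fixed, but the likely harm is limited. Conclusions are unlikely to reverse, because clinically significant results are captured as adverse events and severe values are listed. What would be missing is the incidence of lower-grade and unreported changes, and a clear record of what was dropped. How many subjects that involves cannot be stated from the documents. The conclusion assumes that the table list in 9.1.1 is complete as planned, which is how the SAP presents it.

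**What to change.** Add a laboratory subsection to SAP Section 8 and two tables to 9.1.1, both on the safety population.

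1. Number and percentage of subjects with a treatment-emergent graded laboratory abnormality, by analyte, with any-grade and Grade 3 or 4 rows. Define it as a worst post-baseline CTCAE grade above the Study 205 baseline grade. Baseline matters here: PNH itself causes chronic hemolytic anemia (protocol 5.1), and protocol 12.5.1 recognises that AST and bilirubin can rise with hemolysis, so unadjusted worst grades would mix disease with emergent change. Use scheduled and unscheduled values, as SAP 5.6.6 already allows for most-severe-event analyses, and say that the planned-visit limit in 5.6.7 does not apply to this table.
2. The ALT, AST and bilirubin fold-above-ULN table that protocol 13.3.4 describes.

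In Section 9, name each protocol 13.3.4 analysis that is still dropped, for example the shift tables and by-visit statistics for other analytes. Note there that the Grade 3 or 4 row counts treatment-emergent grades, a qualifier that the protocol's minimum item does not carry. Make the endpoint statements in the SAP technical summary and SAP 2.2 agree.

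The cost is SAP wording and two extra standard tables in an abbreviated report, for at most 30 subjects. Listing 16.2.8 already requires CTCAE grading. No new data and no protocol amendment are needed. If the SAP can no longer be revised, the tables can be added and noted in the study report, which SAP Section 1 provides for.

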### **3. STUDY DESIGN**

#### **3.1. Summary of Study Design**

This study is designed to provide continued access to BCX9930 for subjects currently receiving treatment with BCX9930 in another BioCryst-sponsored clinical study for PNH (i.e., Studies 201, 202, or 203, hereafter referred to as the “prior study”) who, in the opinion of the investigator, have both benefited from treatment with BCX9930 and would benefit from continued treatment with BCX9930, who wish to continue treatment, and who do not have access to other effective treatment options.

Subjects will be eligible to receive study drug (BCX9930) under this version of the protocol for up to 96 weeks for as long as the investigator believes it is in the subject’s best interest to continue treatment, or until the subject has access to another therapy for PNH, whichever comes first. Treatment with BCX9930 will be discontinued for subjects who are deriving no meaningful clinical benefit, or who experience an unacceptable drug-related AE or are otherwise intolerant of study drug.

An independent BCX9930 program-wide DMC will provide oversight of the safety of subjects receiving BCX9930 in this study.

#### **3.2. Definition of Study Treatments**

BCX9930 will be supplied as 100-mg tablets. Subjects will take four BCX9930 100-mg tablets orally BID, approximately 12 hours apart. Study drug may be administered with or without food.

#### **3.3. Sample Size Considerations**

No sample size calculations were conducted for this open-label, long-term safety study. Up to 30 subjects may be enrolled in this study, to allow continued access to BCX9930 following a subject’s participation in another BCX9930 study.

#### **3.4. Randomization**

This is an open-label, non-randomized study.

### **4. PLANNED ANALYSES**

#### **4.1. Interim Analyses**

No formal interim analyses are planned. DMC analysis will be conducted on an as-needed basis.

#### **4.2. Final Analyses**

Analysis of the data will be conducted after all subjects enrolled complete or discontinue the study, the resulting clinical database has been cleaned and quality checked, the analysis populations have been finalized, and the final database lock has occurred.

## 5. GENERAL CONSIDERATIONS FOR DATA ANALYSES AND HANDLING

This section addresses the definitions, algorithms, imputations, and conventions that will apply to the analysis and handling of the data in general. Complex derivations will be addressed in the detailed discussions of individual summary tables.

### 5.1. General Summary Table and Individual Subject Data Listing Considerations

Version 9.4 or higher of the SAS system will be used to analyze the data and to generate tables and listings. All SAS programs prepared to analyze the data will be properly annotated to permit uninvolved outside statistical experts to replicate all the analyses specified in this SAP.

A table of contents for the tables and listings can be found in Section 9.

### 5.2. Statistical Programming

The standard operating procedures (SOPs) of BioCryst will be used. Data will be mapped to Study Data Tabulation Model (SDTM)-compliant datasets prior to creation of Analysis Data Model (ADaM)-compliant derived datasets for use in the creation of summary tables.

### 5.3. Data Presentation Conventions

Summary tables and listings will include “footers” providing:

1. Date and time of output generation.
2. SAS® program name that generates the output.
3. The name(s) and location(s) of any input dataset(s) used in the creation of the output.
4. Any other output-specific details that require elaboration.

The date of output generation links the output to the locked and archived database to allow replication of the results.

### 5.4. Analysis Populations

#### 5.4.1. Safety Population

The safety population is defined as all subjects who receive at least 1 dose of study drug. This population will be used for all analyses of exposure, demographics, and safety.

### 5.5. Baseline Definition

#### 5.5.1. Study Baseline

The last on-treatment visit completed for the prior study will serve as the baseline visit for Study 205. If the baseline visit is missing in the database, the first available measurement from Study 205 will serve as the baseline.

For determination of Hb, ARC, total PNH RBC clone size, the ratio of total PNH RBC clone size to PNH WBC clone size, and haptoglobin, only central lab values that were not impacted by transfusions will be used. Transfusion impacted lab values are those collected within 14 days

after the subject received a pRBC or whole blood transfusion (for Hb, ARC, total PNH RBC clone size and the ratio of total PNH RBC clone size to PNH WBC clone size), or values that are collected within 3 days after the subject received a pRBC or whole blood transfusion (for haptoglobin).

## **5.6. Derived and Transformed Data**

### **5.6.1. Baseline Age**

The subject's baseline age in years will be the age provided in the eCRF as collected at the time of consent.

### **5.6.2. Study Day**

If the date of interest occurs on or after the date of first dose of study treatment, then study day will be calculated as (date of interest – date of first dose) + 1. If the date of interest occurs prior to the date of first dose, then study day will be calculated as (date of interest – date of first dose). There is no study day zero.

### **5.6.3. Change from Baseline and Percent Change from Baseline**

Change from baseline will be calculated as (post-baseline result – baseline result). Percent change from baseline will be calculated as  $(100 \times \text{change from baseline}/\text{baseline result})$ . If either the baseline or the post-baseline result is missing, the change from baseline and percent change from baseline will be set to missing as well. If the baseline value is 0, the percent change from baseline cannot be calculated under this definition. In these cases, percent change will remain missing.

